### 5.8.2 *Prohibited Prior and Concomitant Medication*

Prohibited prior and concomitant medications as outlined in the exclusion criteria (Section 4.2) are the following:

- Short-acting antihistamines or long-acting antihistamines taken must be washed out for the minimum period of time specified in the table in [APPENDIX 4](#) prior to the skin prick testing or to the food challenges;
- Treatment with a high daily dose of inhaled corticosteroid or treatment with a combination therapy of a medium daily dose of inhaled corticosteroid with a long-acting inhaled  $\beta$ 2-agonist or treatment with a combination therapy of a high daily dose of inhaled corticosteroid with a long-acting inhaled  $\beta$ 2-agonist (a list of dosages of inhaled corticosteroids is provided in [APPENDIX 2](#)).
- Two or more systemic corticosteroid courses for asthma taken in the year prior to Visit 1 or 1 oral corticosteroid course for asthma taken within 3 months prior to Visit 1, or during screening period (unless used to treat symptoms triggered by the DBPCFC);
- $\beta$ -blocking agents, angiotensin-converting enzyme inhibitors, angiotensin-receptor blockers, calcium channel blockers or tricyclic antidepressant therapy, during the screening period or during study participation;
- Anti-tumor necrosis factor drugs or anti-IgE drugs (such as omalizumab) or any biologic immunomodulatory therapy taken within 1 year prior to Visit 1, during screening period or during study participation;
- Cyclosporine or other immunosuppressive agents used within 1 year prior to Visit 1, during the screening period or during the study participation. Topical calcineurin inhibitors are permitted,
- Systemic long-acting corticosteroids used within 12 weeks prior to Visit 1 and/or systemic short-acting corticosteroids used within 4 weeks prior to Visit 1 or during screening (unless used for DBPCFC symptoms);
- Any prior or concomitant immunotherapy administered to any food (for example EPIT or OIT or SLIT or specific oral tolerance induction);
- Any aeroallergen immunotherapy administered during study participation.

## 6 VARIABLES AND METHODS OF ASSESSMENT

The efficacy, safety and exploratory endpoints are listed in [Section 3.2](#). The Schedule of Procedures is provided in [Table 7](#).

### 6.1 Efficacy Variables

#### 6.1.1 Response to Treatment – DBPCFC to Peanut

The DBPCFC to peanut will be performed at study entry and post-treatment at Month 12 in order to assess the primary efficacy endpoint (percentage of treatment responders in the active Viaskin® Peanut 250 µg group compared to the placebo group), the main secondary efficacy endpoint (percentage of treatment responders in the active Viaskin® Peanut 250 µg group compared to the placebo group in each screening ED stratum), as well as the other secondary efficacy endpoints (mean and median cumulative reactive/ED of peanut protein and change from baseline at Month 12; percentage of subjects responsive/unresponsive to a cumulative dose  $\geq 1,444$  mg peanut protein at Month 12; percentage of subjects unresponsive to the highest cumulative dose of peanut protein at Month 12).

The DBPCFC is the gold standard to diagnose and assess food allergy. The challenges will occur over 2 days; the subject will be gradually fed increasing amounts of standardized blinded oral formulas containing either peanut protein during one of the two days of the challenge, or without any peanut protein during the other day of the challenge, or vice et versa. Challenges must take place under direct medical supervision in a hospital/clinic setting with resuscitation equipment and emergency medications and staff immediately available. An IV line can be established prior to the challenge when judged necessary by the Investigator. In that case, a local anesthetic cream can be used for establishing the IV line. If a site prefers to have the subjects come to the hospital the day before the conduct of the DBPCFC, to get them ready for the following day, this is allowed and will not be considered an SAE.

Subjects should wash out any antihistamines for the minimum period of time specified in the table in [APPENDIX 4](#)) prior to performing the DBPCFC.

Subjects will not be allowed to use long-acting  $\beta 2$ -agonists within 36 hours prior to the DBPCFC. Subjects who received more than a 3-day course of systemic corticosteroids within 4 weeks of the DBPCFC should have the DBPCFC delayed to allow for 4 weeks of corticosteroid wash-out. If a subject has a reaction during the first day of the DBPCFC that requires treatment with systemic corticosteroids on the first day, the subject has to wait at least 3 days before performing the second day of the DBPCFC.

The subject should have a light breakfast and may drink water at home at least 2 hours before starting the DBPCFC at the site. During the conduct of the challenge, no food other than the challenge formulas should be consumed by the subject. Drinking a sip of water to help swallow the formulas during the challenge, if necessary, is allowed.

After the last dose of the challenge formula is administered, the medical staff should wait at least 1 hour before feeding the subject with any other food and/or water. This first feeding should be light.

A detailed and study-specific Manual of Procedures for the conduct of the DBPCFC will be provided to the Investigators, the site staff and the unblinded study-trained person responsible for reconstituting the formulas. When needed, updated versions will be made available. An outline of the procedures is specified below.

#### *6.1.1.1 Preparation of Peanut and Placebo Formulas*

Standardized formulas, centrally produced by CCI, and packed and released by CCI, will be distributed to all participating centers for the DBPCFC. One of the formulas will be peanut-free (placebo) and the other one will contain peanut protein. An unblinded person identified at each site by the investigator and specifically trained to reconstitute the formulas in the study and not involved in the challenge itself will be responsible for the preparation, adequate labeling and blinding of the pots containing the prepared/hydrated formulas. The blinded pots will then be handed to the medical team to perform the challenge.

#### *6.1.1.2 Time Interval and Doses*

The order of the formulas to be consumed during the first and the second day of the DBPCFC will be determined at random by the unblinded study-trained person preparing the formula using a specific randomization list provided to her/him for this purpose. Other members of the site staff (for example the Investigator, study coordinators, and study nurses), the subject/parents/guardians will remain blinded to the order of consumption until the end of the second day of the DBPCFC. Up to 7 days (1 week) between the 2 days of the DBPCFC will be permitted. The 2 days of the DBPCFC may be 2 consecutive days, but not the same day.

The challenge will consist on giving doses of peanut protein or placebo in gradually increasing doses at 30-minute intervals. This standard interval has been used safely in the past, but the Investigator may use clinical judgment to increase the intervals between doses if there is a concern that an objective reaction may be developing.

The starting dose is 1 mg of peanut protein for the entry/screening DBPCFC as well as the post-treatment DBPCFC; the maximum dose is 300 mg of peanut protein for the entry/screening DBPCFC and 2,000 mg for the post-treatment DBPCFC.

The peanut protein dose increments for the entry/screening DBPCFC are 1 mg, 3 mg, 10 mg, 30 mg, 100 mg, and 300 mg.

The entry/screening DBPCFC challenge is stopped at the 300 mg dose as a maximum, regardless of whether a reaction occurred before or not.

The peanut protein dose increments for the post-treatment DBPCFC are 1 mg, 3 mg, 10 mg, 30 mg, 100 mg, 300 mg, 1,000 mg and 2,000 mg.

#### *6.1.1.3 Entry/screening DBPCFC to Peanut*

Subjects who have not had an objective IgE-mediated reaction leading to stopping the DBPCFC at  $\leq 300$  mg peanut protein will be considered not allergic enough and thus ineligible for this study. Hence, the entry/screening DBPCFC is stopped after the 300 mg dose of placebo or peanut has been dispensed on both days, even if there have been no objective reactions.

Subjects will receive 1 formula (placebo or peanut) on the first day and the other formula (peanut or placebo) on the second day. All subjects will undergo both days of the DBPCFC. The second day of a challenge might not be performed if the subject reacted severely or seriously during the first day of the challenge, leaving no doubt about the nature of the formula administered, which is peanut (i.e. need for intubation, hypotension persisting after epinephrine administration, and/or the need for  $\geq 3$  doses of epinephrine). In this rare case and in this case only, the formula will be unblinded to confirm that the subject received the peanut formula.

At the end of the second day of challenge, the sequence of the 2 formulas given on the 2 days will be unblinded and revealed to the medical staff by the unblinded study-trained person responsible for reconstituting the formulas and the results of the challenge will be established following the decision making algorithm below:

1. The subject had objective IgE-mediated symptoms to the placebo formula at any dose of the challenge. She/he cannot be randomized in the study;
2. The subject had no objective IgE-mediated symptoms during the 2 days of the DBPCFC, neither to the placebo nor to the peanut formulas, even at the 300 mg dose of peanut protein. She/he cannot be randomized in the study;
3. The subject had no objective symptom when receiving placebo but had an objective symptom at 1 of the doses of the peanut formula consumed between 1 mg and 300 mg inclusive. She/he will be randomized in the study in the screening ED stratum that corresponds to the subject's ED.

Only **clear-cut OBJECTIVE immediate-type symptom(s) requiring treatment** will be considered as a reason to stop the challenge and to determine the eliciting dose (highest dose given during the challenge) as well as the Cumulative Reactive Dose (CRD) of peanut protein. **Subjective symptoms will be graded but shall not count to stop the challenge.**

The OFC Symptom Score Sheet in the protocol [APPENDIX 6](#) will be used to score the severity of each symptom (classified under the 5 categories: Skin, Upper respiratory, Lower Respiratory, Gastrointestinal and Cardiovascular/Neurologic).

**More specifically, the food challenge must be stopped if:**

- There is  $\geq 1$ -point rise in an objective symptom from 1 category in the OFC Symptom Score Sheet with the following exceptions:

The followings require a  $>1$ -point rise to stop the challenge if present alone

- Urticaria
- Rash
- Laryngeal (if explained and not persistent)

The followings require a  $>2$ -point rise to stop the challenge if present alone:

- Pruritus
- Sneezing/Itching
- Nasal Congestion
- Rhinorrhea
- Conjunctivitis

- There is  $\geq 1$ -point rise in an objective symptom from  $\geq 2$  categories in the OFC Symptom Score Sheet with the following exceptions:

The following exceptions require a  $\geq 2$  point rise in one of these symptoms plus a  $\geq 1$ -point from another category:

- Pruritus
- Sneezing/Itching
- Nasal Congestion
- Rhinorrhea
- Conjunctivitis

Conjunctivitis (erythema of the conjunctiva) is not mentioned in the OFC Symptom Score Sheet but is an objective symptom that could appear during the challenges and is pre-specified in the e-CRF. Please also report in the e-CRF with a grade when this occurs, together with any other symptoms that could occur during the challenge.

In case of symptoms that develop but do not meet stopping rules, consider allowing 30 additional minutes to see if the reactions subside or progress to meet stopping criteria. You can also repeat the dose or step up at your discretion.

Further details are provided in the study-specific Manual of Procedures for the DBPCFC that will be provided to the sites.

In case of subjective symptoms, for example mouth pruritus, throat pruritus, nausea, abdominal pains or any other subjective symptoms, the severity of which might signify that objective symptoms are developing according to the Investigator's judgment, the time between the previous dose and the next dose might be extended to see how the subject's symptoms evolve. The same dose of peanut protein can be repeated to check whether the subjective symptoms reappear or not and with what severity, or whether objective symptoms now appear. If objective symptoms meeting stopping rules appear, they should be treated and the food challenge will be stopped. The dose given that

triggers the objective symptoms is considered the ED. If only subjective symptoms persist even after the repeated dose, the next planned peanut protein dose is then given to the subject, and the challenge should continue until the appearance of clear objective symptoms meeting stopping rules, at which time the challenge will be stopped and the symptoms treated.

As a safety precaution, the objective symptoms signaling the end of the DBPCFC will be treated. The medication used will be left to the Investigator's judgment.

The Investigator and medical staff will use their own clinical judgment for the most effective treatment to give to the subject considering her/his age, the type of the allergic reactions and their severity. Also refer to recommendations made by Sampson et al. for treating anaphylaxis (42).

Suggested treatments for the different objective symptoms are detailed in the study-specific Manual of Procedures for the DBPCFC provided to the sites.

Should epinephrine need to be administered, it should be injected intramuscularly in the anterolateral thigh using auto-injectors commercially available in each specific site/country. Intravenous epinephrine should NOT be considered at the investigative sites to treat the reactions.

Subjects will be kept under observation for an additional 3 hours after the ingestion of the last dose of the challenge formula. Based on the Investigator's judgment, the observation period could be extended beyond the first 3 hours to ensure that all symptoms have subsided before the subject is discharged. For instance, an overnight stay may be considered necessary by the Investigator if the symptoms have not completely resolved within the 3 hours or if the symptoms have been severe or serious and require longer observation periods.

Complete information for all reactions will be reported first in source documents then in the e-CRF, along with doses given, symptoms observed and their highest grades, time of appearance of the symptoms and an Investigator's assessment of the ED.

#### *6.1.1.4 Post-treatment DBPCFC to Peanut at Month 12*

The DBPCFC at Month 12 is conducted following exactly the same procedures as for the entry/screening DBPCFC. However, it is not stopped at the 300 mg dose. The challenge must instead be continued up to the last dose of 2,000 mg peanut protein or until objective reactions leading to stopping the DBPCFC occur.

Only **clear-cut OBJECTIVE immediate-type symptom(s) requiring treatment** will be considered as a permissible reason to stop the challenge and to determine the eliciting dose (highest dose given during the challenge) as well as the Cumulative Reactive Dose (CRD) of peanut protein. **Subjective symptoms will be graded but shall not count to stop the challenge.** The same instructions provided above to stop the challenge at the entry challenge will be followed to stop the challenge post-treatment.

During the duration of the study, DBPCFCs to other foods cannot be conducted for any randomized subject.

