### 3.3 Justification of the Study Design

This study is designed to assess the efficacy and safety of Viaskin® Peanut 250 µg in children aged 4 through 11 years compared to placebo.

The study design follows the International Conference on Harmonization (ICH) guideline on general considerations for clinical studies (34).

Subject randomization and double-blinding with regard to treatment with Viaskin® Peanut and placebo were chosen in order to prevent bias in treatment allocation and in the assessment of both safety and efficacy. The use of a placebo group in this study is justified to obtain reliable scientific evidence for the evaluation of this new medicinal product.

Peanut allergy is of increasing prevalence in children (3,4,5). It is thus anticipated that the selected pediatric population of peanut allergic subjects will draw a direct benefit from this study.

The DBPCFC is the “gold standard” to diagnose food allergy (35). Since it carries a risk of inducing potentially severe allergic reactions, subjects will be appropriately selected for the challenge, based on their clinical history and peanut-specific IgE test results.

Subjects participating in this study must have a positive DBPCFC at  $\leq 300$  mg of peanut protein. The ED of peanut protein, that is the dose of peanut protein administered to subjects during the DBPCFC procedure which causes an objective allergic reaction leading to stopping the challenge, is capped to 300 mg, with the starting dose of 1 mg. Although the average amount of peanut consumed in an accidental exposure has not been accurately quantified, it is generally believed to be no more than 1 to 2 peanut kernels, or the equivalent of approximately 300 to 600 mg of peanut protein (36,37,38). Thus, this study will enroll subjects who would react at or below 300 mg peanut protein with the objective of inducing desensitization in order to increase significantly the subjects’ threshold levels of peanut.

The selected protein dose of 250 µg for treating peanut-allergic children in this Phase III PEPITES study is based on the safety and efficacy results for children 6 to 11 years of age in the 12-month Phase IIb VIPES study, but also on the safety information from the CoFAR6 study for subjects 4 to 5 years of age (see Sections 1.1.1.2.3 and 1.1.1.2.5).

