##### Cumulative Reactive Dose (CRD)

The cumulative reactive dose of peanut (CRD) will be calculated as follow

CCI

CONFIDENTIAL

Project Document Version No. 3.0

Project Document Effective Date: 04-Oct-2017

Page 32 of 79

- If the ED reported by the investigator in the eCRF is missing, then the CRD is missing
- If the ED reported by the investigator in the eCRF is not missing then the CRD is calculated as the sum of all doses given, including also the repeated and partial doses; doses greater than the ED are not included in the calculation. Example:  
For a particular patient if the set of recorded doses is {1, 3, 10, 30, 100, 300, 300, 1000}, and recorded ED = 300mg, then  $CRD = 1 + 3 + 10 + 30 + 100 + 2 \times 300 = 744mg$ .

No imputation will be performed for other efficacy, safety and exploratory parameters. In those instances observed data will be used, excepted for safety data where partial or missing data will be imputed according to the most conservative approach (See [Section 4.9.1: Adverse Events](#)).

Actual values will be presented in listings.

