#### 4.8.2 Primary Efficacy Analysis

The primary efficacy analysis is based on an endpoint that is derived from the Eliciting dose (ED).

The eliciting dose, i.e. dose at which objective symptoms leading to ending the DBPCFC occurred, is documented by the investigator in the eCRF.

In the following two cases, the ED at the M12 DBPCFC is not documented in the eCRF by the investigator:

- If the M12 DBPCFC is stopped without any objective symptoms leading to ending the DBPCFC (stopping rules) or
- if the subject took the 2,000mg dose without any objective symptom leading to ending the DBPCFC.

In those cases, the last dose given at M12 DBPCFC will be considered for ED value.

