##### Partially ingested dose:

If the last dose given is only partially ingested by the subject prior to the DBPCFC stop, then the ED reported by the investigator is:

- the previous dose given if the quantity of the last dose given actually ingested by the subject is  $\leq$  to the previous dose ingested;
- the last dose given if the quantity of the last dose given actually ingested by the subject is  $>$  than the previous dose ingested.

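### Protocol 6.1.1.3 and 6.1.1.4 gloss the eliciting dose as the highest dose given, but Protocol 3.3 and SAP 4.8.2 use the dose at which the stopping symptoms occurred; the two differ in records the SAP itself provides for

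*Protocol*

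**What the plan says.** **Reading A, highest dose given.** Protocol 6.1.1.4, on the Month 12 challenge, says that only objective symptoms needing treatment count for stopping and "to determine the eliciting dose (highest dose given during the challenge". Protocol 6.1.1.3 has the same parenthesis for the entry challenge.

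**Reading B, triggering dose.** Protocol 3.3 describes the ED as the administered dose "which causes an objective allergic reaction leading to stopping the challenge". Protocol 6.1.1.3, after its list of stopping criteria, says that the dose that "triggers the objective symptoms is considered the ED". SAP 4.8.2 states: "The eliciting dose, i.e. dose at which objective symptoms leading to ending the DBPCFC occurred, is documented by the investigator in the eCRF".

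**SAP supplements to reading B.**
- If the Month 12 challenge ends without stopping symptoms, including after a completed 2,000 mg dose, no ED is entered: "In those cases, the last dose given at M12 DBPCFC will be considered for ED value".
- If the last dose is only partly ingested, the reported ED is "the previous dose given if the quantity of the last dose given actually ingested by the subject is" no more than the previous dose ingested. Otherwise it is the last dose.

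**Where the ED is used.** Protocol 3.2.1.1 and SAP 4.8.2 call a child a responder if the Month 12 ED is at least 1,000 mg (initial ED above 10 mg) or at least 300 mg (initial ED 10 mg or below). SAP 4.8.1.2 sums the doses into the CRD but leaves out any dose above the ED. Its example begins "if the set of recorded doses is {1, 3, 10, 30, 100, 300, 300, 1000}, and recorded ED = 300mg" and arrives at 744 mg. SAP 4.8.3.5 counts a child as responsive when the CRD is at least 1,444 mg.

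**The concern.** The investigator enters the ED in the eCRF, and the primary endpoint is derived from it. The protocol gives sites two descriptions of what to enter, and they are not equivalent. The SAP shows that its authors expected records in which they differ: it has a rule for doses above the ED and an example containing one. SAP 4.13, which lists departures from the protocol, revises the handling of challenges that end without stopping symptoms but does not mention the parenthesis in 6.1.1.3 and 6.1.1.4. The partial-dose rule is described as what the investigator reports, yet the protocol contains no such rule.

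At stake is the input to the responder classification, and through the ED also the CRD and the 1,444 mg endpoint. The SAP recalculates the CRD but takes the recorded ED as given, and it describes no check of that ED against the doses given. A site that followed the parenthesis would pass its reading straight into the analysis.

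**Working it through.** **Inputs.** Doses and recorded ED: SAP 4.8.1.2. Responder thresholds: Protocol 3.2.1.1 and SAP 4.8.2. The 1,444 mg cut-off: SAP 4.8.3.5. Month 12 dose steps of 1, 3, 10, 30, 100, 300, 1,000 and 2,000 mg: Protocol 6.1.1.2.

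**Step 1: reproduce the SAP's figure.** CRD = sum of recorded doses not above the ED. With ED = 300 mg:
1 + 3 + 10 + 30 + 100 + 300 + 300 = 744 mg, as the SAP states.

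**Step 2: same record under the parenthesis.** The highest dose given is 1,000 mg, so ED = 1,000 mg and CRD = 744 + 1,000 = 1,744 mg.

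**Step 3: apply the endpoints.**

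| | Reading B: ED 300 mg | Reading A: ED 1,000 mg |
|---|---|---|
| CRD | 744 mg | 1,744 mg |
| CRD at least 1,444 mg | no | yes |
| Screening ED 1, 3 or 10 mg (threshold 300 mg) | responder | responder |
| Screening ED 30, 100 or 300 mg (threshold 1,000 mg) | non-responder | responder |

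The cut-off is the cumulative dose through 1,000 mg without repeats: 1 + 3 + 10 + 30 + 100 + 300 + 1,000 = 1,444 mg.

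**Step 4: which one-step differences matter.** If the highest dose given is one step above the triggering dose, responder status changes in only two situations:
- trigger 300 mg, highest 1,000 mg, screening ED above 10 mg;
- trigger 100 mg, highest 300 mg, screening ED 10 mg or below.

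Every other adjacent pair leaves the classification unchanged. The plan expects about 2/3 of children to have a screening ED of 30 to 300 mg (Protocol 4.5.2).

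**Step 5: partial dose.** Take, for illustration, a child who completes 300 mg and then swallows 200 mg of the 1,000 mg dose. Since 200 is not more than 300, SAP 4.8.2 gives ED 300 mg. The parenthesis, if given means offered, gives 1,000 mg. With screening ED above 10 mg, status changes as in Step 3.

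**Step 6: size per record.** At the planned 220 and 110 children, one reclassified child moves its arm's response rate by 1/220 = 0.45 or 1/110 = 0.91 percentage points. The number of such records is not stated, so no total follows.

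**Step 7: planned position against the 15% rule.** At 40% v 10% (88/220 v 11/110), the Wilson lower limit for active is 0.3375 and the upper limit for placebo is 0.1702. The Newcombe lower bound is 0.30 − √[(0.40 − 0.3375)² + (0.1702 − 0.10)²] = 0.30 − 0.094 = 0.206, or 20.6%.

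**The case against.** The parenthesis stands in a sentence about challenges stopped for objective symptoms, and Protocol 6.1.1.3 requires stopping once the criteria are met. In an ordinary challenge no dose follows the triggering one, so the highest dose given is the triggering dose. This stands: the two readings differ only in exceptional records.

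The analysis also has a stated rule. SAP 4.8.2 uses the triggering dose, with fallbacks for challenges without stopping symptoms and for partial doses, and the CRD rule follows from it. This stands too. What remains open is the value entered at the site, not the analyst's algorithm.

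The example illustrates how the CRD is summed. It gives no screening ED and no responder status, so a reader who infers that it flips the primary endpoint outright goes too far. The flip needs a screening ED above 10 mg.

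At entry, a shift from 10 to 30 mg would change both the subgroup and the threshold. The documents show no such record, and the entry ED is fixed before randomization, so knowledge of treatment cannot make it differ by arm.

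Sites also receive a Manual of Procedures for the challenge, not available here, which may settle how the ED is recorded. If it does, it still disagrees with one protocol passage or another.

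**Conclusion.** The inconsistency is real and reaches the primary endpoint, but only through records with a dose above the ED or a partly ingested last dose. For the SAP's example the consequence is exact: CRD 744 v 1,744 mg, across the 1,444 mg cut-off, and a change from non-responder to responder if the screening ED was above 10 mg. With screening ED 10 mg or below, responder status does not change. The effect on the difference in response rates cannot be computed, because the frequency of such records and their split by arm are not given.

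Two stronger readings are not supported:
- **Bias towards one arm.** A reader might infer that visible patch-site reactions, more frequent on active, would sway how investigators assign the ED. No passage links skin reactions to ED recording, and the investigator's attribution would remain under either definition.
- **A decisive effect on the trial.** A reader might infer that a single reclassified child could settle the result. That holds only for counts chosen next to the 15% boundary. At the planned rates the lower bound is 20.6%.

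The conclusion assumes that sites could act on the protocol text as written.

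**What to change.** These changes concern endpoint derivation only; the challenge stopping rules stay as they are.

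1. Reconcile the parenthesis in Protocol 6.1.1.3 and 6.1.1.4 with the SAP 4.8.2 definition, so that one definition, including the partial-dose rule, applies at both challenges. The rule for challenges without stopping symptoms should be stated as well. It matters only at Month 12, because a child without such symptoms at entry is not eligible. Check that the Manual of Procedures agrees.
2. At the blinded data review already planned in SAP 4.4, before unblinding, list and query every record in which a dose above the recorded ED was given or the last dose was partly ingested, for both the entry and the Month 12 challenge. Record each resolution in the review minutes. If the challenges are already complete, this step does the work and step 1 only documents the rule.

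I would not add a sensitivity analysis with the ED set to the highest dose given. It would score children on the definition being removed and credit doses given after the eliciting one.

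Cost: one clarification and a few data queries.
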